# 9.4.3. Electrocardiogram

An ECG will be taken locally at screening to determine subject eligibility for participation in the study.

During the collection of ECGs, subjects should be in a quiet setting without distractions (eg, television, cell phones). Subjects should rest in a supine position for at least 5 minutes before ECG collection and should refrain from talking or moving arms or legs. If blood sampling or vital sign measurement is scheduled for the same time point as ECG recording, the procedures should be performed in the following order: ECG(s), vital signs, blood draw.

Twelve-lead ECGs will be recorded until 4 regular consecutive complexes are available so that the different ECG intervals (RR if available, PR, QRS and QT) and heart rate can be measured. The QT intervals will be corrected for heart rate according to Bazett's (QTcB) and Fridericia's (QTcF) QT corrections.

Any clinically relevant findings at screening must be recorded in the AE section of the eCRF.

## 9.4.4. Vital Signs

Systolic and diastolic blood pressure (SBP, DBP), pulse rate (supine after at least 5 minutes rest), and weight will be recorded in a quiet setting without distractions, at the time points specified in the Time and Event Schedule.

Blood pressure and pulse/heart rate measurements will be assessed with a completely automated device if possible. Manual techniques will be used only if an automated device is not available.

To obtain the actual body weight, subjects should be weighed lightly clothed.

Any clinically relevant findings at screening and changes occurring during the study must be recorded in the AE section of the eCRF.

# 9.4.5. Physical Examination

Complete physical examinations, or symptom-directed physical examinations (physical examination for which symptoms have been reported by the subject) as needed, will be performed at the time points in the Time and Event Schedule.

A complete physical examination includes skin and mucous membranes, lymph nodes, respiratory system, cardiovascular system, abdomen, central nervous system, peripheral nervous system, musculoskeletal system, genitourinary system and head-neck examination. Urogenital or anorectal examination will be performed at the discretion of the investigator if clinically relevant. Subjects should be undressed during these complete physical examinations, which should be performed by a licensed medical doctor, a physician's assistant or a nurse practitioner in accordance with local guidelines.

The height should be measured barefooted at the screening visit.

Any clinically relevant findings at screening and changes occurring during the study must be recorded in the AE section of the eCRF.

## 9.4.6. Bone Investigation Substudy

A bone investigation substudy will be performed at selected study sites, to assess bone biomarkers and DXA scans, in at least 170 subjects (85 in each treatment arm) who provide informed consent for the substudy.

DXA scans will be performed in subjects participating in the DXA substudy, provided that all necessary local regulatory authority and ethics committee approvals have been obtained. DXA scans will be performed at the time points specified in the Time and Event Schedule and will cover the spine and hip to measure changes in BMD.

A complete description of the procedures for the DXA scans will be provided in the DXA manual.

Reading of the DXA scans will be performed centrally and results will be sent to the investigator. The investigator must review the DXA scan report, document this review and record any clinically relevant findings at baseline and changes occurring during the study in the AE section of the eCRF. The DXA scan reports must be filed with the source documents. For the management of potential bone toxicity, see Section 9.4.6.

In subjects participating in the DXA substudy, blood will be collected for assessment of bone biomarkers (including CTX, P1NP, PTH and 25-hydroxy vitamin D) at the time points specified in the Time and Event Schedule.

# 9.5. Toxicity Management

The toxicity management guidelines in this section are applicable throughout the entire study, starting from baseline through the 96-week treatment period and the extension phase.

General guidance for the management of toxicities is provided in Section 9.5.1. Guidance for specific toxicities is provided in Sections 9.5.2 through 9.5.9. Please, see also Sections 9.4 and 12 for information on procedures concerning the measurement and reporting of clinically relevant abnormalities and toxicities.

Any questions regarding toxicity management should be directed to the sponsor's medical monitor.

# 9.5.1. General Guidance for the Management of Clinical Events and Laboratory Abnormalities

#### Grade 1 and 2

Continue study medication at the discretion of the investigator.

#### Grade 3

- For a grade 3 clinical event or clinically relevant laboratory abnormality, study medication may be continued if the event is considered to be unrelated to study medication.
- For a grade 3 clinical event, or clinically relevant laboratory abnormality confirmed by repeat testing (see Section 9.4.2), that is considered to be related to study medication, study medication should be withheld until the toxicity returns to baseline or within 1 grade from baseline, ie, ≤ grade 2.
- Mandatory confirmation is not warranted for asymptomatic grade 3 glucose elevations in subjects with pre-existing diabetes, and asymptomatic grade 3 triglyceride or cholesterol elevations.
- If a laboratory abnormality recurs to ≥ grade 3 following rechallenge with study medication and is considered related to be to study medication, study medication should be permanently discontinued and the subject managed according to local practice. Recurrence of laboratory abnormalities considered unrelated to study medication may not require permanent discontinuation

#### Grade 4

• For a grade 4 clinical event or clinically relevant laboratory abnormality confirmed by repeat testing (see Section 9.4.2), that is considered to be related to study medication, study medication should be permanently discontinued and the subject managed according to local practice. The subject should be followed as clinically indicated until the laboratory abnormality returns to baseline or is otherwise explained, whichever occurs first. A clinically relevant grade 4 laboratory abnormality that is not confirmed upon repeat testing should be managed according to the algorithm for the new toxicity grade.

- Mandatory confirmation is not warranted for asymptomatic grade 4 glucose elevations in subjects with pre-existing diabetes, and asymptomatic grade 4 triglyceride or cholesterol elevations.
- Study medication may be continued without dose interruption for a clinically nonrelevant grade 4 laboratory abnormalities (eg, grade 4 CPK after strenuous exercise, or triglyceride elevation that is nonfasting or that can be medically managed), or a clinical event considered unrelated to study medication.

A schematic overview of these guidelines is provided in Attachment 3 for clinically relevant laboratory toxicities.

#### 9.5.2. Cutaneous Events/Rash

DRV is a sulfonamide. Subjects who previously experienced a sulfonamide allergy will be allowed to enter the study. To date, no potential for cross-sensitivity between drugs in the sulfonamide class and DRV has been identified.

Cutaneous events/rash should be captured in the AE section of the eCRF.

Management will be at the discretion of the investigator, taking into account the following protocol-defined procedures (see also Table 3), and should follow generally accepted medical standards. Cetirizine, levocetirizine, topical corticosteroids, and antipruritic agents will be allowed at the investigator's discretion for treatment of all grades of rashes.

### **Grade 1 and 2 Cutaneous Reaction/Rash**

A grade 1 cutaneous reaction/rash is defined as localized rash.

A grade 2 cutaneous reaction/rash is defined as diffuse rash or target lesions.

Subjects experiencing a grade 1 or 2 rash or cutaneous event may continue treatment, or have their study medication interrupted at the investigator's discretion. Safety sampling (to be processed by the central laboratory) at the time of the rash and clinical follow-up for these AEs will be at the discretion of the investigator, however, close clinical follow-up is recommended to monitor for any progression of the AE.

#### Grade 3 and 4 Cutaneous Reaction/Rash

A grade 3 cutaneous reaction/rash is defined as:

• Diffuse rash with vesicles or limited number of bullae or superficial ulceration of mucous membrane limited to 1 site.

For the purpose of this study, the sponsor considers qualifying as a grade 3 rash:

- Cutaneous reaction/rash with at least 1 of the following:
  - elevations of ALT/AST > 2 x baseline but  $\geq$ 5 x ULN;

- fever  $\ge$ 38°C or 100°F;
- serum sickness-like reaction;
- eosinophil count >1,000/mm^3.
- The syndromes of DRESS and AGEP.

A grade 4 cutaneous reaction/rash is defined as:

- Extensive or generalized bullous lesions;
- Stevens-Johnson syndrome (SJS);
- Ulceration of mucous membrane involving at least 2 distinct mucosal sites;
- TEN.

Subjects experiencing a grade 3 or 4 rash or cutaneous event must have their study medication discontinued. Referral to a dermatologist and biopsy are required for these events preferably within 24 hours after the site becomes aware of the cutaneous event/rash.

Safety testing (to be processed by the central laboratory) of the following parameters is required to determine possible liver or systemic abnormalities: ALT, AST, bilirubin (total, direct and indirect), creatinine and a hematology profile. Close clinical follow-up and appropriate medical intervention should be instituted for these events; daily follow-up is recommended for 5 days from the onset of the event to monitor for progression of the event and weekly afterwards as long as grade 3 or 4 rash is present. Once grade 3 or 4 rash has resolved to  $\leq$  grade 2 rash, follow-up should be done according to the instructions for grade 1 or 2 rash.

Table 3: Summary of Cutaneous Reaction/Rash Follow-up

DAIDS Toxicity Grade	Definitions	Investigator Action	
Grade 1	Localized rash	Subject may continue study medication	
Grade 2	Diffuse rash	Subject may continue study	
	Target lesions	medication	
Grade 3	Diffuse rash with vesicles or limited number of bullae	Permanently discontinue study medication	
	Superficial ulcerations of mucous membrane limited to 1 site	Referral to a dermatologist and biopsy, preferably within 24 hours after the site becomes aware of the cutaneous event/rash  Laboratory assessments need to be	
	For the purpose of this protocol, the sponsor considers qualifying as a grade 3 rash the following:		
	Cutaneous reaction/rash with at least 1 of the following:	performed	
	- Elevations in ALT and/or AST (>2 x baseline but ≥5 x ULN) - Fever ≥38°C or 100 F - Serum sickness-like reaction - Eosinophils >1,000/mm³		
	DRESS and AGEP		
Grade 4	Extensive or generalized bullous lesions SJS	Permanently discontinue study medication	
	Ulceration of mucous membrane involving at least 2 distinct mucosal sites TEN	Referral to a dermatologist and biopsy, preferably within 24 hours after the site becomes aware of the cutaneous event/rash	
		Laboratory assessments need to be performed	

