### Determining Severity Grade

If the severity of an AE could fall under either 1 of 2 grades (eg, the severity of an AE could be either grade 2 or grade 3), select the higher of the 2 grades for the AE.

Laboratory normal ranges should be taken into consideration to assign gradings to a laboratory value.

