Fever (non-axillary temperatures only)	38.0 to <38.6°C or 100.4 to <101.5°F	≥38.6 to <39.3°C or ≥101.5 to <102.7°F	≥39.3 to <40.0°C or ≥102.7 to <104.0°F	≥40.0°C or ≥104.0°F
Pain  (not associated with study agent injections and not specified elsewhere)  Specify location	Pain causing no or minimal interference with usual social & functional activities	Pain causing greater than minimal interference with usual social & functional activities	Pain causing inability to perform usual social & functional activities	Disabling pain causing inability to perform basic self-care functions OR Hospitalization indicated
Serum Sickness 	Mild signs and symptoms	Moderate signs and symptoms AND Intervention indicated (eg, antihistamines)	Severe signs and symptoms AND Higher level intervention indicated (eg, steroids or IV fluids)	Life-threatening consequences (eg, requiring pressor or ventilator support)
Underweight  >5 to 19 years of age	NA	WHO BMI z-score <-2 to ≤-3	WHO BMI z-score <-3	WHO BMI z-score <-3 with life-threatening consequences
2 to 5 years of age	NA	WHO Weight-for- height z-score <-2 to ≤-3	WHO Weight-for- height z-score <-3	WHO Weight-for- height z-score <-3 with life-threatening consequences
<2 years of age	NA	WHO Weight-for- length z-score <-2 to ≤-3	WHO Weight-for- length z-score <-3	WHO Weight-for- length z-score <-3 with life-threatening consequences

Definition: A disorder characterized by nausea, headache, tachycardia, hypotension, rash, and/or shortness of breath.

http://www.who.int/growthref/who2007\_bmi\_for\_age/en/ for participants >5 to 19 years of age and http://www.who.int/childgrowth/standards/chart\_catalogue/en/ for those ≤5 years of age.

<sup>10 For pain associated with injections or infusions, see the *Site Reactions to Injections and Infusions* section.

<sup>11 Definition: A disorder characterized by fever, arthralgia, myalgia, skin eruptions, lymphadenopathy, marked discomfort, and/or dyspnea.

 WHO reference tables may be accessed by clicking the desired age range or by accessing the following URLs:

PARAMETER	GRADE 1 MILD	GRADE 2 MODERATE	GRADE 3 SEVERE	GRADE 4 POTENTIALLY LIFE- THREATENING

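### The fever limit that makes a rash grade 3 is printed as 38°C or 100°F, which are different temperatures, so sites reading different scales would act differently from 37.8 to below 38.0°C

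*Protocol*

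**What the plan says.** Section 9.5.2 of the protocol adds sponsor-specific features to the standard definition of a grade 3 rash, introduced by "For the purpose of this study, the sponsor considers qualifying as a grade 3 rash". A rash with any one of them qualifies. The fever feature appears in Table 3 as "Fever ≥38°C or 100 F", and the body text above the table gives the same two values.

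The grade decides what happens next:

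- **Grade 3 or 4.** "Subjects experiencing a grade 3 or 4 rash or cutaneous event must have their study medication discontinued"; Table 3 makes the stop permanent. "Referral to a dermatologist and biopsy are required for these events", preferably within 24 hours of the site learning of the event, and central-laboratory safety tests are also required.
- **Grade 1 or 2.** Subjects with a "grade 1 or 2 rash or cutaneous event may continue treatment", or the investigator may interrupt it. Safety sampling is discretionary, and "close clinical follow-up is recommended to monitor for any progression of the AE".

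The DAIDS table in Attachment 1 grades fever as an adverse event in its own right. Its grade 1 range is "38.0 to <38.6°C or 100.4 to <101.5°F".

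**The concern.** A threshold printed in two units should be one threshold. Here the two figures are different temperatures, and fever alone is enough to move a grade 1 or 2 rash to grade 3. Between the two figures, the protocol both requires and does not require a permanent stop with referral and biopsy, depending on which number the site reads.

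What is at stake is the consistent management of individual subjects. Two sites could see the same rash at 37.9°C and act differently, each following a number printed in the protocol. One subject would lose study drug and have a biopsy. The other could stay on treatment under observation.

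**Working it through.** **Inputs.** The limits of 38°C and 100°F come from Section 9.5.2 (text and Table 3). The DAIDS fever limits come from Attachment 1. The sign ≥ is printed once, before 38°C, and is taken to apply to both figures.

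**Formulas.** °F = °C × 9/5 + 32, and °C = (°F − 32) × 5/9.

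**Step 1: do the printed values agree?**

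- 38 × 9/5 + 32 = 68.4 + 32 = 100.4°F, not 100°F.
- (100 − 32) × 5/9 = 340/9 = 37.78°C, not 38°C.
- The gap is 100.4 − 100 = 0.4°F, or 38 − 37.78 = 0.22°C.

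**Step 2: where do the two limits disagree?**

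| Temperature | In °F | Meets ≥38°C | Meets ≥100°F |
|---|---|---|---|
| 37.7°C | 99.86 | no | no |
| 37.8°C | 100.04 | no | yes |
| 37.9°C | 100.22 | no | yes |
| 38.0°C | 100.40 | yes | yes |

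The band of disagreement holds two readings on a 0.1°C scale (37.8 and 37.9) or four on a 0.1°F scale (100.0, 100.1, 100.2 and 100.3).

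**Step 3: how does the protocol pair the scales elsewhere?** The DAIDS fever row gives both units at each grade boundary:

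| DAIDS boundary | Converted | Printed °F |
|---|---|---|
| 38.0°C | 100.40°F | 100.4 |
| 38.6°C | 101.48°F | 101.5 |
| 39.3°C | 102.74°F | 102.7 |
| 40.0°C | 104.00°F | 104.0 |

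All four agree to one decimal. This row grades fever, not rash, and so does not set the rash limit. It is used here only to show the correct partner of 38.0°C.

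**Step 4: could this be a text-extraction artefact?** The same two values stand in the body text and in the table. Only the degree sign before F is missing in the table, and that changes nothing.

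**The case against.** **It is one threshold with a rounded Fahrenheit value.** The DAIDS fever row joins equivalent values in the two units with the word or. On that usage the rash rule means 38°C, and 100°F is 100.4°F cut to a whole degree. This is the most natural account of how the error arose, and it stands as such. It does not remove the problem, because a site working in Fahrenheit sees 100 and has no reason to look for a missing decimal.

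**A stronger reading a reader might infer.** Taken as two alternative criteria, the pair would make 100°F the limit that governs and leave 38°C with no function, since every temperature of at least 38°C is also at least 100°F. The documents do not support going that far. The DAIDS row shows the word joining unit equivalents. Attachment 1's instruction, when an event could fall in either of two grades, to "select the higher of the 2 grades for the AE" is general DAIDS guidance and does not settle a threshold that the sponsor set for this study. The supportable statement is that the two figures are inconsistent.

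**There are safeguards.** Section 9.5.2 leaves management to the investigator's discretion in light of the protocol-defined procedures and accepted medical standards. Below the limit the investigator may still interrupt drug and take samples. Section 9.5 sends toxicity questions to the sponsor's medical monitor. So a borderline febrile rash is not left unmanaged on either reading. But the grade 3 actions are mandatory, and a site that reads only its own scale sees a clear limit and nothing to ask about.

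**Divergence between sites is not shown.** This is fair. SAP Section 2.4.1 lists Europe and North America as regions, which suggests that both scales may be in use, but no document says which scale any site uses. Temperature is not among the vital signs in Section 9.4.4, and the rash rule names no measurement route.

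**Conclusion.** The point holds as an internal inconsistency in a decision threshold, and it is minor. The two printed values differ by 0.4°F (0.22°C). They give different mandatory actions only for a rash with no other grade 3 feature and a temperature from 37.8 to below 38.0°C (100.0 to below 100.4°F). The documents do not give the number of such cases. It is likely to be small, because the band is narrow and temperature is not measured on schedule.

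The arithmetic and the difference in required action rest on the documents alone. That sites would in practice diverge rests on the assumption that both temperature scales are in use.

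A reader might also infer an effect on the trial's results, since discontinuation for an adverse event counts as non-response under the snapshot rules in SAP Section 4.1.3 (written there for Week 96). The documents do not support that step. They give no count of affected rashes, the same rule applies to both arms, and treatment is blinded through the primary analysis. No effect on the primary endpoint or on the analysed adverse event grades is claimed.

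**What to change.** Print one matched limit in the Section 9.5.2 text and in Table 3. The value most consistent with the rest of the protocol is ≥38.0°C (≥100.4°F). If the sponsor confirms that the lower trigger was intended, it should read ≥37.8°C (≥100°F). Either choice closes the band. Sites should be told the value, because the toxicity rules apply through Week 96 and the extension phase.

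The cost is one value corrected in two places and a site notice, with no new data collection. Amendment 2, classed as non-substantial, already corrected a misprinted power figure, so there is a precedent for a correction of this kind.

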## 9.5.3. Acute Systemic Allergic Reaction

Management will be at the discretion of the investigator, taking into account the following protocol-defined procedures (see also Table 4), and should follow generally accepted medical standards.

#### Grade 1

A grade 1 acute systemic allergic reaction is defined as localized urticaria (wheals) with no medical intervention indicated.

Subjects may continue study medication or have their study medication interrupted at the investigator's discretion. The subject should be advised to contact the investigator immediately if there is any worsening of the pruritus, or if any systemic signs or symptoms develop. Antihistamines or topical corticosteroids or antipruritic agents may be prescribed as long as these are in line with the (dis)allowed medications as indicated in Section 8 or the local Prescribing Information of the ARVs.

#### Grade 2

A grade 2 acute systemic allergic reaction is defined as localized urticaria with medical intervention indicated, or mild angioedema with no intervention indicated.

Subjects may continue study medication or have their study medication interrupted at the investigator's discretion. If there is any worsening of the allergic reaction, the subject should be advised to contact the investigator immediately and to discontinue study medications. Antihistamines or topical corticosteroids or antipruritic agents may be prescribed as supportive care as long as these are in line with the (dis)allowed medications as indicated in Section 8 or the local Prescribing Information of the ARVs.

#### Grade 3

A grade 3 acute systemic allergic reaction is defined as generalized urticaria, or angioedema with intervention indicated or symptoms of mild bronchospasm.

Subjects will permanently discontinue study medication. Subjects will be treated as clinically appropriate. Standard management should be undertaken.

#### Grade 4

A grade 4 acute systemic allergic reaction is defined as acute anaphylaxis, or life-threatening bronchospasm, or laryngeal edema.

Subjects will permanently discontinue study medication. Subjects will be treated as clinically appropriate. Standard management should be undertaken.

**Table 4:** Summary of Allergic Reaction Follow-up

DAIDS Toxicity Grade	Definitions	Investigator Action
Grade 1	Localized urticaria (wheals) with no medical intervention indicated	Subject may continue study medication
Grade 2	Localized urticaria with intervention indicated, or mild angioedema with no intervention indicated	Subject may continue study medication
Grade 3	Generalized urticaria, or angioedema with intervention indicated, or symptoms of mild bronchospasm	Permanently discontinue study medication
Grade 4	Acute anaphylaxis, or life-threatening bronchospasm, or laryngeal edema	Permanently discontinue study medication

